Otago physiotherapy laboratories. Health care providers (those directly referring to the study, study coordinator, treating physiotherapists) involved in recruitment, screening and treatment of participants will be asked to attend focus groups and individual interviews immediately following completion of treatment sessions by the final participant (“*nested qualitative data collection*”). These will be conducted via zoom or face-to-face depending on any COVID -19 related health restrictions at the time, and also participant preference.

Recruitment:

Procedure: Potential participants will include 160 acutely concussed adults (aged 18-60 years; biological sex: male, female) and are subjects to be considered for this ethics application. Participants for initial screening using the SPE will be recruited via advertisement and or referral (provision of study details) from local primary health care providers.

Local primary health care providers will include but are not limited to Student Health Services, and physiotherapy outpatient, concussion, and balance clinics at the University of Otago, as well as local (Dunedin greater area) physiotherapy clinics specialising in management of concussion. University of Otago electronic and physical notice boards including social media sites (the Researcher’s Twitter accounts, School of Physiotherapy Clinics Facebook, University of Otago Instagram accounts) and a research webpage created on the website of the Centre for Health, Activity and Rehabilitation Research (CHARR), School of Physiotherapy will be used for recruitment via advertisement. A link to the Participation Information Sheet will be contained within the social media posts and webpage link to the created research webpage.

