neck post-concussion [18] and with recommendations regarding pilot data sample sizes [19] so is considered adequate for this feasibility study.

Screening and Eligible Participant Identification Process:

Screening session procedure: The screening session will take place at the School of Physiotherapy research laboratories and will be conducted by the PI. Prior to attending the screening session participants will be sent a link by the SC to complete the battery of online questionnaires and asked to complete them 1 day prior to attendance. Included in the battery will be an electronic version of the consent form which participants will be required to sign prior to being able to access the questionnaires.

Questionnaires:

- Rivermead Post-concussion Symptoms Questionnaire (RPQ) [20] *13 Item and 3 Item* – Originally developed to provide an overall symptom severity measure based on symptom reporting following concussion. Participants rate the degree to which each symptom poses more of a problem since their head injury on a 0 to 4-point scale. When divided into three and thirteen item symptom scales construct validity was calculated at 0.83 for the 13-item questionnaire and 0.62 for the 3-item. IRR was 0.89 and 0.72 respectively [21]
- Neck Disability Index (NDI) [22] a 10 item scaled questionnaire. Each question requires the participant to select a response which most accurately reflects the difficulty they experience with specific functional tasks such as driving, reading working or sleeping, and also the extent to which they experience difficulty with function due to headache. It is currently utilised in cervical dysfunction populations including Whiplash Associated Disorder and neck pain to identify functional limitations resulting from either condition. Test-retest reliability has been established at 0.89 [22].
- Dizziness Handicap Index (DHI) [23] lists 25 functional activities. Individuals are asked to rate how much dizziness or unsteadiness affects performance of listed activities in terms of frequency. When summed the greatest resultant total scores for each of the subcategories; functional, emotional, or physical is determined to be the underlying causes for dizziness. Interrater reliability for the DHI has been calculated at 0.97 and internal consistency established between 0.72 and 0.85 for each of the categories [23]

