Participants identified as eligible for entry to treatment arm: will include those participants who demonstrate positive findings for a minimum of 3 cervical spine musculoskeletal and or sensorimotor outcome [12] as well as an absence of 2 or more positive oculomotor indicators of vestibulo-ocular impairment [55, 57]

Participants identified as ineligible for entry to treatment arm: identified due to an absence of sufficient positive neck related physical assessment findings, or alternately a positive

vestibulo-ocular screen will be provided with standardised graduated return to activity information [14, 70] as well as appropriate referral where evidence of vestibulo-ocular or physiological impairment is identified by the SC.

Of note, the SC conducting the laboratory-based screening session will be a New Zealand registered physiotherapist, and hold a current annual practicing certificate, Physiotherapy New Zealand membership, and ACC registration. They will hold additional training in OMT with a minimum of 3 years clinical experience. They will also have received specialised training from the PI (OG) in assessments to be used during the screening session including performance of testing, data reduction, and analysis of quantifiable outcomes necessary to establish participant eligibility for enrolment in the treatment arm of the study.

Estimated duration of total testing time will be 1.25 hour (1 hour for the SPE and 0.25 hours for induction and consent). All participants who provide consent and complete the SPE will be provided with a \$40 voucher to recognise the reasonable costs involved with participating in this study.

Treatment Sessions:

Treatment sessions procedure:

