Up to 10 health practitioners involved in the referring, assessing, and treating of study participants will be invited to participate in focus groups (n=2, 5 participants per group). They will be asked to complete a brief demographic questionnaire (including questions related to age, biological sex, number of years and scope of practice). Four of these individuals will be further invited to attend one-on-one semi-structured interviews. Focus groups will be used to determine health practitioner attitudes toward ease of use (including any challenges), and perceived effectiveness (acceptability and usefulness) of the SPE to identify individuals

appropriate for neck rehabilitation (Orthopedic Manual Treatment (OMT) and neuromuscular/sensorimotor retraining) following concussion, and utility of this method in the context of current practice. All focus group and interviews will be recorded using a digital voice recorder, which will be transcribed for analysis. All transcriptions will be checked and anonymised by the SC. Based on coding and thematic analysis of transcribed recordings of focus group proceedings the study team will iteratively determine main themes to be further explored in semi-structured interviews. Co-investigators of the study will conduct all focus groups and interviews. All academic members of the study team have experience in qualitative research.

Focus groups and interviews will be held at the University of Otago research rooms. Prior to participation in the focus groups, attending health practitioners will have the purposes of the focus group/ interviews explained and will provide written consent. All participants will be reimbursed at \$120 per hour voucher to recognise the reasonable costs involved with participating in this study. Reimbursement for attendance at interviews will be provided in addition to reimbursement for attendance at focus groups.

Outcome Measures and Analysis:

Primary Outcomes: Feasibility

Qualitative data: focus groups and interviews

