We will use Thematic Analysis, an evaluative deductive approach to analyse the qualitative focus group and interview data, as described by Clarke and Braun [77]. The SC will code each transcription and one of the researchers will code every third transcription, grouping the codes into themes and sub-themes. An iterative process will be used within the research team to define the main themes and emerging models related to the study aims. In this way thematic analysis will be reflexive to aid in identification of any instances where the PI's beliefs may unduly influence identification of these main themes.

Quantified feasibility outcomes: activity, compliance, and adverse event monitoring

Participants will record daily performance of home exercises prescribed by the treating therapist in an activity-log (yes/ no, minutes of exercise per day) to determine treatment compliance. Non-attendance at scheduled treatment sessions will be recorded by the treating therapist (yes/no per session) as well as any adverse reactions to treatment (number). Participants will complete an exiting questionnaire to assess patient satisfaction [78].

Experimental Outcomes:

Experimental outcome measures (experimental studies a. & b.) will include but are not limited to:

Category	Exploratory OM
Cervical Spine	

Kinematic Assessment - Virtual Reality	Total range of motion (deg) Peak Velocity – Rotation R (deg/s) Peak Velocity – Rotation L (deg/s) Peak Velocity – Rotation Ext. (deg/s) Global head motion accuracy (deg)
Muscle Function (CFET)	Total time (sec)
Manual Spinal Examination	Pos/ neg
Sensorimotor Function (JPE)	Degrees Error (deg) Neck Disability Index (tot/ 50) Headache Impact Test-6
Vestibulo-Ocular	
VNG OM Assessment	Full Assessment (≥ 2 pos/neg overall (pos/neg) ; pos/neg per assessment)
VOMS assessment	Increase in symptoms (11- point NRS) ; avg NPC > 5cm Dizziness Handicap Index
Participant Outcomes	
Physical Activity : Actigraphy	Minutes of Vigorous Physical Activity, min/day Physical Activity (TAC/d; steps/d; PAEE - kcal/kg/day) Activity log Consensus Sleep Diary PROMIS sleep questionnaires IPAQ (METs) Fatigue Severity Scale
Quality of Life	EuroQol-5D-5L (EQ VAS)

Data Management

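### The study coordinator is both a planned focus-group and interview informant and the person who anonymises and codes every transcript, and nothing keeps the two roles apart

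*Protocol*

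**What the plan says.** **Informant role.** Study Procedure and Setting defines the providers to be approached for the qualitative work: "those directly referring to the study, study coordinator, treating physiotherapists) involved in recruitment, screening and treatment of participants will be asked to attend focus groups". The same sentence goes on to individual interviews. Nested Qualitative Focus Groups and Interviews draws its informants from those who refer, assess and treat participants.

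**Size of the qualitative component.** Up to 10 practitioners "will be invited to participate in focus groups (n=2, 5 participants per group"), and "Four of these individuals will be further invited to attend one-on-one semi-structured interviews". Coding of the focus groups sets the themes to be followed up in the interviews, so the focus groups come first.

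**Transcript handling.** The same section states: "All transcriptions will be checked and anonymised by the SC". Co-investigators, not the SC, run all the sessions.

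**Coding.** Under Outcome Measures and Analysis, in the paragraph on qualitative data: "The SC will code each transcription and one of the researchers will code every third transcription". The research team then settles the main themes iteratively. The paragraph closes by presenting this as a reflexive check on undue influence from the PI's beliefs, and it does not mention the SC.

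**Status of the outcome.** These data fall under the primary feasibility outcomes, and the Study Objectives section names clinician attitude to the simplified physical examination (SPE) among the primary outcomes.

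**The concern.** Coding turns what informants said into the units from which themes are built. If the coder is also an informant, the coder decides how their own remarks are labelled and how much weight they get beside the remarks of others in the room. As checker and anonymiser, the same person also handles colleagues' identifiable transcripts before anyone else, which could reduce candour.

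At stake is whether the provider-attitude component of the feasibility conclusion can be read as independent of one informant's view. The protocol already accepts that a team member's beliefs can distort themes, but it applies that reasoning only to the PI and not to the person who codes everything.

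**Working it through.** The plan states no figure to reproduce. The check sets the roles side by side and counts transcripts.

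**1. Roles given to the SC**

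| Role | Where in the Protocol | Is the SC excluded anywhere? |
|---|---|---|
| Asked to be an informant | Study Procedure and Setting | No |
| Checks and anonymises all transcripts | Nested Qualitative Focus Groups and Interviews | No |
| Codes all transcripts | Outcome Measures and Analysis, qualitative data | No |
| Covered by the reflexivity check | Same paragraph | Only the PI is named |

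Nothing bars the SC from coding a session in which the SC took part.

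**2. Planned transcripts.** Assuming one transcript per session and full uptake: 2 focus groups + 4 interviews = 6.

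**3. Transcripts with a second coder.** Every third of six: 6 / 3 = 2, wherever the sequence starts. Coded by the SC alone: 6 − 2 = 4, and 4 / 6 = 67%. If only one to three interviews take place, this share lies between 50% and 80%, depending on the starting point.

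**4. Transcripts that can contain the SC's own words.** The SC would sit in one focus group and could be one of the four interviewees: at most 1 + 1 = 2 of 6 (33%). As a share of focus-group informants, the SC is 1 of up to 10 (10%).

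**5. Do the sets in steps 3 and 4 coincide?** Nothing in the plan makes them. With six transcripts in time order, focus groups first:

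| Start of sequence | Double-coded transcripts | Focus groups double-coded |
|---|---|---|
| First | 1 and 4 | one of two |
| Second | 2 and 5 | one of two |
| Third | 3 and 6 | none |

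If the third and sixth are taken, both focus groups, including the SC's, are coded by the SC alone, and those codes set the interview agenda.

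**6. Does the overlap depend on who performs the SPE?** No. The Screening session procedure says: "The screening session will take place at the School of Physiotherapy research laboratories and will be conducted by the PI". Eligibility for Entry to Treatment Arm instead refers to "the SC conducting the laboratory-based screening session will be a New Zealand registered physiotherapist". Data Management and Data storage lean towards the SC. The conflict is unresolved, but Study Procedure and Setting names the SC as an informant in either case.

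**The case against.** The best defence is that the SC is not the only analyst. Co-investigators conduct the sessions, the team determines the themes, a second researcher codes part of the material, and overall feasibility comes from triangulating qualitative with quantitative results. The SC is only asked to attend, so participation is planned, not certain. All of this stands and limits the effect. It does not remove the overlap, because for transcripts without a second coder the team works from codes that only the SC produced.

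Some stronger readings are tempting, but the document does not support them:

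- **That the SC codes colleagues' opinions of the SC's own examinations.** This needs the SC to perform the SPE, on which the protocol contradicts itself.
- **That 67% measures the conflict.** It is the share without a second coder. The SC's own words reach at most about a third of the transcripts.
- **That themes will be pushed in a favourable direction.** The SC had yet to be appointed, and no stake in the result is stated. A coordinator close to a demanding examination could equally stress its difficulties.
- **That clinician attitude is the leading primary outcome.** It is listed with compliance and satisfaction, without ranking.
- **That the SC edits transcripts.** The stated tasks are checking and anonymising.
- **That every transcript must be double-coded.** Partial double-coding is a declared choice, and wanting more is a preference.

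**Conclusion.** The point holds as a role conflict that the protocol itself sets up: the person who anonymises and codes all the transcripts is also a planned informant, and the reflexivity check does not cover that person. It directly affects at most about 2 of 6 planned transcripts, neither of which is certain to have a second coder. This rests on full uptake, one transcript per session, and the SC accepting the invitation.

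The consequence is a risk of bias of unknown direction in one component of a primary feasibility outcome, partly mitigated by the session and theme arrangements. It is a modest weakness, worth correcting because it can be settled cheaply before coding begins.

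**What to change.** Choose one of two routes:

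1. **Remove the SC from the informants** in Study Procedure and Setting. The cost is one informant of up to 10.
2. **Keep the SC as an informant, but not as handler of those sessions.** A co-investigator who is not an informant checks, anonymises and codes any transcript in which the SC speaks (at most about one focus group and one interview). These transcripts are placed among the double-coded ones, with a second coder other than the SC. The protocol says that all academic team members have qualitative experience, so no new staff are needed. The planned coding load is 6 + 2 = 8 transcript codings. If the two second codings go to these transcripts, the total stays at 8: two codings and two rounds of checking and anonymising move from the SC to a co-investigator.

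Reporting the SC's statements separately is not advisable. The study has a single coordinator, so this would identify the speaker and defeat the anonymisation.

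Under either route, extend the reflexivity statement in the qualitative data paragraph to the SC, and reconcile Screening session procedure with Eligibility for Entry to Treatment Arm on whether the PI or the SC conducts the screening session. Both are text changes.

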Volunteers who: respond to advertisement i) using the online screening questionnaire relating to the inclusion/exclusion criteria (primarily whether they have sustained a medically diagnosed concussion within the last 14 days); ii) the study phone; iii) the study email, or who are referred by a health practitioner will be contacted by the study SC. The SC will further screen them for inclusion and exclusion criteria. If eligible to participate in the screening session participants will be forwarded an electronic participant information sheet and consent form and scheduled for the screening session. Individuals contacting the SC in response to advertising who meet exclusion criteria at any stage of the screening process will be provided with names and contact details of primary health services for concussion in Dunedin for follow up if desired. Those recruited via advertisement will be requested to obtain written confirmation of their concussion from their treating physician.

Inclusion criteria: Adults aged 18-60 years, biological sex: male, female, who have sustained a medically diagnosed concussion (mild Traumatic Brain Injury) based on published diagnostic criteria [13-15] and are not more than 14 days since injury [14].

Exclusion criteria: Individuals with past or current history of:

- Moderate to severe TBI as defined by published diagnostic criteria [16]
- Diagnosed concussion with associated trauma related abnormalities apparent on CT or MRI and/ or cervical spine fracture
- Diagnosed concussion due to assault
- Neck pain unrelated to concussion injury(/ies) (requiring treatment)
- Headache disorders (including cervicogenic, migraine (chronic), and tensions type headaches)
- Vestibular, oculomotor, neurological disorders
- Major psychiatric disorders currently being actively treated
- Physical injury that would prevent completion of the screening session

Study power:

Based on previously identified rates of neck impairment post-concussion [9, 17] it is anticipated that screening of **160** participants will be required to identify **60** individuals who meet inclusion criteria. Allowing for 50% of individuals to decline participation in the trial and a 10% drop-out rate, it is anticipated that data from **n=27** participants (treatment commenced with **n=30**) will be collected at all data collection time points. This group size is consistent with those currently used in randomised control trials investigating outcome following OMT of the

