Video Nystagmography (VNG) Vestibulo-ocular Assessment: This includes various tests where the participant while wearing a pair of goggles with an implanted video camera (GN Otometrics ICS Impulse® video nystagmography unit), will be asked to focus their eyes on certain positions on a blank wall 1m in front of them while their head is moved by the assessor, or they move it independently. Additionally, the subject's eyes will be covered momentarily for some tests. These clinical assessments are commonly used to assess for any dysfunction which may indicate the presence of disturbance to usual eye reflexes [59, 60]. In this case the addition of the VNG goggles allows results to be quantified, increasing diagnostic utility of the measures [61]

Dix Hallpike manoeuvre and Head-roll tests currently used clinically to assess for the presence of BPPV will also be performed using the VNG goggles. The manoeuvre is performed with the individual sitting on a plinth with legs extended and head turned to the side by about 45 degrees. The individual is then quickly assisted into a lying position by the tester, with the head and neck fully supported and remaining rotated and in approximately twenty degrees of extension. Onset of involuntary eye movement is then observed (specialised goggles which black out the room, also often used clinically, will be used for observational purposes) to determine the presence of BPPV [62]. Sensitivity and specificity for this are established [62]. Currently accepted testing procedure requires the performance of the test once for accurate diagnosis. The eyes are covered throughout the test so that visual fixation on an object by the participant does not occur.

Vestibular Oculomotor Screen: The Vestibular Ocular Motor Screen (VOMS) [63] is a test designed for use with individuals aged 9-40, interpretation of abnormal results in individuals outside this age range may vary. While interpretation of results is based on symptom reproduction, abnormal movements of the eyes should also be recorded. Where oculomotor (OM) movements seem abnormal and so it seems you have detected OM or vestibular

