Treating physiotherapists will be New Zealand registered, and hold current annual practicing certificates, Physiotherapy New Zealand membership, and ACC registration. They will hold additional training in OMT to at least diploma level with a minimum of 5 years clinical experience. Treating therapists will also participate in an initial 1 x 3 hour study induction session followed by 2 x 1 hour follow-up study review sessions (April to August). These sessions will be conducted by the PI (OG), a Masters (Musculoskeletal Physiotherapy) qualified physiotherapist, with 20+ years of clinical experience and expertise treating disorders of the neck including concussion, who is registered with the PNZ, and holds a current APC, and ACC registration. Sessions will provide physiotherapists treating patients in the study with an opportunity for continuing education related to concussion management. All sessions will be in person.

Follow up sessions:

Procedure:

Following completion of the treatment protocol all participants will be contacted by the SC and scheduled for follow-up review sessions (1 week and 3 months following completion of treatment sessions or if treatment sessions were not completed in full per-protocol follow up times). Follow-up sessions will be held at the same laboratories attended for the screening session. Participants will be requested to complete the same battery of questionnaires 1 day prior to attending each time and will also be examined using the SPE on both occasions. Participants will also be administered with activity monitors at each follow up and asked to wear these for a further 7 days and complete the daily activity and sleep logs. All participants completing these follow up sessions will be provided with a \$40 voucher to recognise the reasonable costs involved with participating in this study.

Nested Qualitative Focus Groups and Interviews:

Procedure:

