Linear mixed method analysis of repeated experimental outcomes will determine treatment effect. Effect modifiers including sex and age as well as statistically significant demographic confounders will be included in the final model. Further secondary analysis may be undertaken using data collected at all time points. Multivariable linear regression will identify items of the VOMS which best predict VNG OM.

Data storage:

All data (including patient and health practitioner data) will be stored on the personal password-protected laptops of the PI ([name]) and or the password-protected study laptop. Any hard copies of the questionnaires and consent forms will be stored in the PI's office in a secure filing cabinet. Only the researchers mentioned in the application and the SC (tba) responsible for processing and analysis will have access to the de-identified data collected during the study. The principal researcher ([name]) and the SC will keep a list identification codes with participant names, so that participants can be identified by their coded data if needed.

A standardised hard copy of the summary report of the participants findings from the screening session completed by the SC will be provided to the treating physiotherapist (via postal mail). This will not be de-identified since it will be used by the treating physiotherapist to inform treatment. A copy of these reports will be kept on the PI's personal password-protected laptop.

The treating physiotherapist will record the clinical assessment and treatments, as required, on their usual practice management systems as well as information related to study feasibility.

All data will be stored for the duration of the study on the primary investigator's password-protected University laptop and will be accessible by members of the research team. It will also be stored for at least 10 years in the school's archive folder on the High-Capacity Storage System (HCSS). Any personal information held about the participants (such as contact details and hard copy questionnaires) may be destroyed at completion of the research. Coded study information may be kept by the University of Otago in secure, cloud-based storage indefinitely. All storage will comply with NZ I data security guidelines.

Potential problems: (medical/legal; issues with disclosure; conflict of interest, etc)

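### Near point of convergence is listed only as above or below 5 cm; if analysed in that form, change on one side of the cut cannot register and the item may predict less well

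*Protocol*

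**What the plan says.** The table under Experimental Outcomes has one row for the VOMS, which reads "Increase in symptoms (11- point NRS) ; avg NPC > 5cm", followed by the dizziness questionnaire. No entry gives NPC in centimetres. Other measured quantities in the table keep their own units: degrees for range of motion, head motion accuracy and joint position error, degrees per second for peak velocity, and seconds for flexor endurance.

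The list is open: "Experimental outcome measures (experimental studies a. & b.) will include but are not limited to". The paragraph on the Vestibular Oculomotor Screen does not describe how NPC is taken, how many trials are averaged, or what the 5 cm limit is for. It says only: "While interpretation of results is based on symptom reproduction, abnormal movements of the eyes should also be recorded".

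Under Follow up sessions, participants "will also be examined using the SPE on both occasions", that is, 1 week and 3 months after treatment ends. The VOMS is described within the Simplified Physical Examination, so NPC is a repeated measure.

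Statistical Analysis, Objective 2, names two analyses: "Linear mixed method analysis of repeated experimental outcomes will determine treatment effect" and "Multivariable linear regression will identify items of the VOMS which best predict VNG OM". Neither sentence says in which form NPC enters.

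**The concern.** An average distance is a number on a continuous scale, and adding a limit turns it into yes or no. As a repeated outcome in that form, a participant who moves from 12 cm to 6 cm shows no change, while one who moves from 5.1 cm to 4.9 cm changes category. As a predictor, every distance above 5 cm is treated alike.

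The Study Objectives include validating an objective clinical oculomotor screen. NPC is the one listed VOMS outcome that is not a symptom rating, and it is listed in two categories while the symptom ratings keep an 11-point scale. What is at stake is how well Objective 2 can use this one item. No feasibility criterion is touched.

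**Working it through.** **The plan's own figures.** Study power states that "screening of 160 participants will be required to identify 60 individuals who meet inclusion criteria", and continues: "Allowing for 50% of individuals to decline participation in the trial and a 10% drop-out rate". Then 60 × (1 − 0.50) = 30 start treatment and 30 × (1 − 0.10) = 27 have data at all time points. This matches the stated 30 and 27. The protocol gives no mean, standard deviation, distribution or share above 5 cm for NPC, so everything numerical below is illustration.

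**What the cut does to change.** Score 1 if NPC is above 5 cm and 0 otherwise (hypothetical values):

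| Before | After | Change in cm | Change in score |
|---|---|---|---|
| 12 | 6 | −6 | 1 to 1: none |
| 9 | 5.5 | −3.5 | 1 to 1: none |
| 5.1 | 4.9 | −0.2 | 1 to 0 |

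This needs no distributional assumption.

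**Fit to the planned models.** A linear mixed model assumes roughly normal residuals with a variance that does not depend on the mean. A 0/1 outcome has variance p(1 − p), which changes with the mean, and fitted values can leave the range 0 to 1. The Statistical Analysis section plans normality tests and transformation of skewed data. That can help a distance in centimetres; no transformation makes a two-valued variable normal.

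**Information kept by a cut, measure taken once.** Assume a normal measure with a linear relation to the other variable and a share p above the cut. The information kept is φ(z)² / [p(1 − p)], with z the normal quantile at 1 − p and φ the normal density.

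- p = 0.50: z = 0, φ = 0.3989, kept = 0.1592 / 0.25 = 0.637, lost 36%.
- p = 0.30: z = 0.524, φ = 0.3477, kept = 0.1209 / 0.21 = 0.576, lost 42%.
- p = 0.20: z = 0.842, φ = 0.2800, kept = 0.0784 / 0.16 = 0.490, lost 51%.
- p = 0.10: z = 1.282, φ = 0.1755, kept = 0.0308 / 0.09 = 0.342, lost 66%.
- p = 0.05: kept = 0.224, lost 78%.

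The formula is symmetric, so 80% above the cut loses as much as 20% above.

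**A paired illustration.** The formula is not a repeated-measures result, so two visits were also simulated: 27 participants, normal values, within-person correlation 0.5, a true shift of 0.5 SD, two-sided 5% tests, 20,000 replicates. Power in the original units was 0.70. With the yes/no score it was 0.36 (paired t) or 0.27 (exact McNemar) when half start above the cut, and 0.24 or 0.10 when 20% do. These inputs are assumptions, and the simulation is simpler than the planned three-visit model.

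**The case against.** The strongest reply is that the table is only a list of exploratory outcomes, expressly not exhaustive. Objective 2 does not say which form of NPC enters either model, it leaves room for secondary analyses, and coding is often settled in a statistical analysis plan, which is not at hand. The 5 cm limit may simply name an abnormality criterion, like the two-or-more rule in the VNG row above it. A fixed limit also has a use in a clinical screen whose reference result is itself positive or negative; if the true relation to that reference is a step, cutting NPC may cost little. All of this stands as a limit on the point, which is conditional on the listed form being the one analysed. It does not remove the fact that this is the only form the protocol specifies.

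Three stronger readings are tempting and not supported:

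- A reader might infer that the cut hides change in both Objective 2 analyses. The VOMS regression predicts VNG findings and does not analyse change; there the possible cost is a weaker predictor, and nothing shows that the item would be dropped.
- A reader might take a loss of a third to a half as established. It rests on assumed normality and on 20% to 80% lying above 5 cm. Normality is doubtful: a distance cannot be negative, so a normal NPC centred at 5 cm, with zero 2 SD below the mean, has an SD of about 2.5 cm. A value of 12 cm would then lie (12 − 5) / 2.5 = 2.8 SD out. Data with many such values would be skewed, and the percentages would not apply.
- A reader might turn the percentages into effective sample sizes, such as 0.637 × 27 = 17.2 or 0.637 × 160 = 101.9. These fit neither analysis. Loss for change depends on within-person correlation and on how many participants cross the cut. Loss for a predictor depends on its overlap with other VOMS items and the shape of the relation. The protocol also does not say that all 160 enter the regression.

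**Conclusion.** The point holds in a conditional form and is minor. If the listed form is analysed, the mixed model is blind to change on one side of 5 cm and is fitted to a kind of outcome it does not suit, and NPC may be a weaker predictor of VNG findings. The size cannot be fixed from the protocol. The 36% (half above the cut) to 51% (20% above) applies only to a normal measure taken once, and the loss grows as the share moves further from one half. Participants with two or more positive oculomotor indicators do not enter treatment, so a low share above 5 cm in the treated group is plausible but not established. The primary feasibility outcomes and their 80% criteria are unaffected.

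**What to change.** In the Experimental Outcomes table, replace the NPC entry with average NPC in centimetres. Use that value, transformed if skewed as the Statistical Analysis section already provides, as the repeated outcome in the mixed model and as the predictor in the VOMS-VNG regression. Keep the share of participants above 5 cm as a descriptive percentage at each visit, which preserves its clinical reading. The cost is one table entry. An average implies that the distance is already being recorded, so no new measurement should be needed, though the data form should be checked to confirm that it stores the distance and not only the category.
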